**Not applicable**

The paper survey will be administered after the final update has been received by the family in the waiting area. A member of the research team will deliver the survey to the family member, and there will be a collection box in the waiting area for the completed surveys. There will be no identifying information on the survey. The survey will be administered only once per family, and it has a total of six questions.

**Statistical Considerations:** Delineate the precise outcomes to be measured and analyzed. Describe how these results will be measured and statistically analyzed. Delineate methods used to estimate the required number of subjects. Describe power calculations if the study involves comparisons. Perform this analysis on each of the primary and secondary objectives, if possible.

We will be examining the relationship between patient families' levels of anxiety and satisfaction with the number of updates received during the perioperative period. We will include a minimum of 96 participants, with 48 cases in each study group. This study sample was chosen using previous data collected in a similar study. Although this study did not administer surgical updates at specific time points, as we propose, they used a similar method of analyzing anxiety and satisfaction levels. Using their mean anxiety ratings, along with the standard deviations, a power analysis revealed that for a power of 0.8 with a significance of 0.05, the proposed study will require a total of 96 participants.

**Risks/Benefits:** Describe any potential or known risks. This includes physical, psychological, social, legal or other risks. Estimate the probability that given risk may occur, its severity and potential reversibility. If the study involves a placebo or washout period, the risks related to these must be addressed in both the protocol and consent. Describe the planned procedures for protecting against or minimizing potential risks and assess their likely effectiveness. Where appropriate, discuss plans for ensuring necessary medical or professional intervention in the event of adverse effects to the subjects. Discuss the potential benefits of the research to the subjects and others. Discuss why the risks to the subjects are reasonable in relation to the anticipated benefits to subjects and others. Discuss the importance of the knowledge gained or to be gained as a result of the proposed research and why the risks are reasonable in relation to the knowledge that reasonably may result. If there are no benefits state so.

There are no potential risks of this study. The survey does not require the subjects to report any identifying information. The data from this study will allow us to evaluate whether satisfaction and anxiety may be reduced with timely updates. This information can then be used to improve patient and family satisfaction in the perioperative period.

**Therapeutic Alternatives:** List the therapeutic alternatives that are reasonably available that may be of benefit to the potential subject and include in the consent form as well.

**Not Applicable**

**Data Safety and Monitoring:** The specific design of a Data and Safety Monitoring Plan (DSMP) for a protocol may vary extensively depending on the potential risks, size, and complexity of the research study. For a minimal risk study, a DSMP could be as simple as a description of the Principal Investigator's plan for monitoring the data and performance of safety reviews or it could be as complex as the initiation of an external, independent Data Safety and Monitoring Board (DSMB). The UVM/UVM Medical Center process for review of adverse events should be included in the DSMP.

The Principal Investigator will perform safety reviews annually.

**Adverse Event and Unanticipated Problem (UAP) Reporting:** Describe how events and UAPs will be evaluated and reported to the IRB. All protocols should specify that, in the absence of more stringent reporting requirements, the guidelines established in the Committees on Human Research "Adverse Event and Unanticipated Problems Reporting Policy" will be followed. The UVM/UVM Medical Center process for review of adverse events and UAPs to subjects or others should be included in the DSMP.

All guidelines established in the Committees on Human Research "Adverse Event and Unanticipated Problems Reporting policy" will be followed.

**Withdrawal Procedures:** Define the precise criteria for withdrawing subjects from the study. Include a description of study

requirements for when a subject withdraws him or herself from the study (if applicable).

If the family decided not to complete the survey after the surgery is complete, they will be removed from the study population.

**Sources of Materials:** Identify sources of research material obtained from individually identifiable human subjects in the form of specimens, records or data. Indicate whether the material or data will be obtained specifically for research purposes or whether use will be made of existing specimens, records or data.

Research material will be obtained from the administered survey

## DRUG AND DEVICE INFORMATION

Investigators are encouraged to consult the UVM Medical Center Investigational Pharmacy Drug Service ([name]) prior to finalizing study drug/substance procedures.

**Drug (s)**  **Not applicable**

Drug name – generic followed by brand name and common abbreviations. Availability – Source and pharmacology; vial or product sizes and supplier. If a placebo will be used, identify its contents and source. (attach investigational drug brochure)

Preparation: Reconstitution instructions; preparation of a sterile product, compounded dosage form; mixing guidelines, including fluid and volume required. Identify who will prepare.

Storage and stability – for both intact and mixed products.

Administration – Describe acceptable routes and methods of administration and any associated risks of administration.

Toxicity – Accurate but concise listings of major toxicities. Rare toxicities, which may be severe, should be included by indicated incidence. Also adverse interactions with other drugs used in the protocol regimen as well as specific foods should be noted. Address significant drug or drug/food interactions in the consent form as well. List all with above details.

Is it FDA approved: (include FDA IND Number)

1. in the dosage form specified? If no, provide justification for proposed use and source of the study drug in that form.

2. for the route of administration specified? If no, provide justification for route and describe the method to accomplish.

3. for the intended action?

**Device (s)**  **Not applicable**

Device name and indications (attach investigational device brochure)

Is it FDA approved: (include FDA IDE Number)

1. for indication specified? If no, provide justification for proposed use and source of the device.

Risk assessment (non-significant/significant risk) - PI or sponsor needs to assess risk of a device based upon the use of the device with human subjects in a research environment.

## SUBJECT CHARACTERISTICS, IDENTIFICATION AND RECRUITMENT

**Subject Selection:** Provide rationale for subject selection in terms of the scientific objectives and proposed study design.

Subjects will include family members of orthopaedic surgical patients. We believe that the role of surgeon-family communication and periodic updates play an increased role on family members' anxiety and satisfaction during surgeries of longer duration, so surgeries lasting less than two hours will not be included in the study. We will also exclude patients under the age of 18 years old and non-English speaking patients and/or families to ensure that consent is valid.

**Vulnerable Populations:** Explain the rationale for involvement of special classes of subjects, if any. Discuss what procedures or practices will be used in the protocol to minimize their susceptibility to undue influences and unnecessary risk (physical, psychological, etc.).

**Not applicable**

**Number of Subjects:** What is the anticipated number of subjects to be enrolled at UVM/UVM Medical Center and in the case of a multi-center study, with UVM/UVM Medical Center as the lead, the total number of subjects for the entire study.

There will be a minimum of 96 subjects. We anticipate approximately 200, and all subjects will be enrolled at UVM/UVM Medical Center.

**Inclusion/Exclusion Criteria:** Eligibility and ineligibility criteria should be specific. Describe how eligibility will be determined and by whom. Changes to the eligibility criteria at a later phase of the research have the potential to invalidate the research.

Inclusion criteria includes all families of orthopaedic surgical patients of the surgeons involved in this research study. Exclusion criteria include surgeries lasting less than two hours, patients under the age of 18 years old, and non-English speaking patients and/or families. Each orthopaedic surgical case will be reviewed for eligibility prior to the surgery date by a member of the research team.

**Inclusion of Minorities and Women:** Describe efforts to include minorities and women. If either minorities or women are excluded, include a justification for the exclusion.

Women and minorities will be included, given that they meet inclusion criteria listed above.

**Inclusion of Children:** Describe efforts to include children. Inclusion is required unless a clear and compelling rationale shows that inclusion is inappropriate with respect to the health of the subjects or that inclusion is inappropriate for the purpose of the study. If children are included, the description of the plan should include a rationale for selecting or excluding a specific age range of children. When included, the plan must also describe the expertise of the investigative team in working with children, the appropriateness of the available facilities to accommodate children, and the inclusion of a sufficient number of children to contribute to a meaningful analysis relative to the purpose of the study. If children are excluded then provide appropriate justification. Provide target accrual for this population.

Patients under the age of 18 are excluded from this study. Communication with families during the time of surgery is different for pediatric patients than for adult patients. For example, parents are often able to escort children into the operating room.

For protocols including the use of an investigational drug, indicate whether women of childbearing potential have been included and, if not, include appropriate justification.

N/A

If HIV testing is included specifically for research purposes explain how the test results will be protected against unauthorized disclosure. Include if the subjects are to be informed of the test results. If yes, include the process and provision for counseling. If no, a rationale for not informing the subjects should be included.

**Not applicable**

**Recruitment:** Describe plans for identifying and recruitment of subjects. All recruitment materials (flyers, ads, letters, etc) need to be IRB approved prior to use.

PI/Collaborators will recruit their own patient's and their families

## FINANCIAL CONSIDERATIONS

**Expense to Subject:** If the investigation involves the possibility of added expense to the subject (longer hospitalization, extra studies, etc.) indicate in detail how this will be handled. In cases where the FDA has authorized the drug or device company to charge the patient for the experimental drug or device, a copy of the authorization letter from the FDA or sponsor must accompany the application. Final approval will not be granted until the IRB receives this documentation.

There are very limited circumstances under which study participants may be responsible (either directly or via their insurance) for covering some study-related expenses. If the study participant or their insurer(s) will be billed for any portion of the research study, provide a justification as to why this is appropriate and acceptable. For example, if the study involves treatment that is documented standard of care and not investigational, state so. In these cases, the protocol and the consent should clearly define what is standard of care and what is research.

N/A

**Payment for participation:** Describe all plans to pay subjects, either in cash, a gift or gift certificate. Please note that all payments must be prorated throughout the life of the study. The IRB will not approve a study where there is only a lump sum payment at the end of the study because this can be considered coercive. The amount of payment must be justified. Clarify if subjects will be reimbursed for travel or other expenses.

**Not applicable**

**Collaborating Sites.** When research involving human subjects will take place at collaborating sites or other performance sites when UVM/UVM Medical Center is the lead site, the principal investigator must provide in this section a list of the collaborating sites and their Federalwide Assurance numbers when applicable. (agreements may be necessary)

**Not applicable**

### **INFORMED CONSENT**

**Consent Procedures:** Describe the consent procedures to be followed, including the circumstances under which consent will be obtained, who will seek it, and the methods of documenting consent. Specify the form(s) that will be used e.g. consent (if multiple forms explain and place identifier on each form), assent form and/or HIPAA authorization (if PHI is included). These form(s) must accompany the protocol as an appendix or attachment.

**Note:** Only those individuals authorized to solicit consent may sign the consent form confirming that the prospective subject was provided the necessary information and that any questions asked were answered.

On the day of the surgery, a research team member will inform the patient and family that a study is being conducted to investigate the effect of perioperative communications on family satisfaction and anxiety. Consent will be implied upon the completion of the survey. No PHI is included in this study.

**Information Withheld From Subjects:** Will any information about the research purpose and design be withheld from potential or participating subjects? If so, explain and justify the non-disclosure and describe plans for post-study debriefing.

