Prior to the surgery, a member of the research team will review each case to determine if the surgery meets study criteria. The exclusion criteria include: surgeries lasting less than two hours, patients under the age of 18, non-speaking patients and/or families, or patients that do not have family members present in the pre-operation area. On the day of the surgery, a research team member will inform the patient and family that a study is being conducted to investigate the effect of perioperative communications on family satisfaction and anxiety. It will be explained that each family will randomly be assigned to two communication pathways, and there will be a short survey for them to complete post-surgery. In the control pathway, the surgeon will communicate with the family per his/her usual practice near the completion of the surgical procedure. In the intervention group, the families will receive additional standardized electronic updates via pagers at three pivotal moments: 1) Initial skin incision has been made, 2) Critical part of the case is completed and closure has begun, 3) Closure is complete, and patient is about to be transferred to the recovery room. A member of the surgical team will be responsible for sending these updates. Then, the surgeon will communicate the final update near the end of the surgical procedure per his/her usual practice.

After the surgery is complete, and both control and intervention groups have received the final update, a research team member will locate the waiting family and administer the post-operative survey rating their satisfaction and anxiety levels using Likert scale questions (1-5 scale). We adopted a previously used survey and modified it accordingly. In addition to the survey, basic demographic information of the patient and family member completing the survey, as well as the number of people in the waiting party, will be reported. When the family member has completed the survey, they will leave the survey in a secure drop box in the waiting area.

To ensure that the results of the survey are reproducible, we will take twenty subjects who completed the survey and ask permission to call them one day after the initial survey. We will then compare the results of the two surveys.

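### The only act defined as consent is completing the post-operative survey, so refusals can fall after allocation, when families know their pathway, and may differ by arm

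*Combined protocol and SAP*

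**What the plan says.** The relevant statements are spread over several sections of the protocol.

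- **Before surgery.** Consent Procedures says that on the day of surgery "a research team member will inform the patient and family that a study is being conducted". The Procedures section adds the randomisation: "It will be explained that each family will randomly be assigned to two communication pathways". It also mentions the later survey. Neither section describes asking for or recording agreement at this conversation.
- **During surgery, intervention arm only.** "the families will receive additional standardized electronic updates via pagers at three pivotal moments: 1) Initial skin incision has been made", followed by pages when closure begins and when it is complete. The surgeon's usual update follows in both arms.
- **Survey.** It is given "After the surgery is complete, and both control and intervention groups have received the final update".
- **Consent.** "Consent will be implied upon the completion of the survey".
- **Refusal.** Withdrawal Procedures: "If the family decided not to complete the survey after the surgery is complete, they will be removed from the study population".
- **Sample size.** Statistical Considerations: "We will include a minimum of 96 participants, with 48 cases in each study group", for power 0.8 at significance 0.05. Number of Subjects anticipates about 200. No refusal rate or allowance is given, and no count of non-completers by arm is planned.

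**The concern.** Treating a completed form as consent suits a stand-alone survey. This study also randomises families and gives one arm a communication pathway that the other does not get. The act that counts as consent, and so admits a family to the analysis, comes at the very end.

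The statistical difficulty is where refusals fall. A refusal before assignment cannot depend on the arm. A refusal after surgery can: families have been told there are two pathways and know whether they were paged. The outcomes are satisfaction and anxiety, which could plausibly affect willingness to fill in a form. Dropping non-completers then conditions the comparison on something the intervention may have changed. With no pre-assignment record and no count by arm, a family that never wished to take part cannot be told from one put off by its experience, and a reader cannot judge whether the arms lost different families.

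**Working it through.** **1. Order of events.** Putting Procedures, Consent Procedures and Withdrawal Procedures together:

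1. Patient and family are informed.
2. The family is assigned at random. The moment is not stated, but the first page goes out at skin incision, so assignment must precede it.
3. Pages are sent (intervention arm).
4. The surgeon gives the final update (both arms).
5. The survey is offered.
6. Completion is taken as consent; a family that declines is removed.

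The one refusal point written into the plan is therefore after allocation and after the whole intervention. By contrast, Procedures does describe asking permission for the next-day repeat telephone survey; nothing comparable is written for assignment.

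**2. The plan's own figure.** The total of 96 cannot be reproduced, because the means and standard deviations behind it are not given. Working back from 48 per arm with a two-sided 5% test and 80% power (sidedness is an assumption):

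d = (1.960 + 0.842) × √(2/48) = 0.572 SD (0.578 with the t-test; 0.508 or 0.511 if one-sided).

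This is circular and does not confirm 96. It only supplies a scale for what follows.

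**3. Bias from selective refusal.** Let r be the refusal rate in an arm and k the refuser-minus-completer difference in SD. The mean of all assigned families is the completer mean plus r × k, so the completer mean is off by r × k. With the same k in both arms:

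bias = (r_control − r_intervention) × k.

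Type I error is the chance that a two-sided 5% z-test rejects when the true difference is zero and the observed one is shifted by this bias, with SE = √(1/n₁ + 1/n₂) and n = 48 × (1 − r). All rates and values of k are assumptions.

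| Refusal, control / intervention | k (SD) | Bias (SD) | Share of 0.572 | Type I error |
|---|---|---|---|---|
| 10% / 10% | 1.0 | 0 | 0% | 5.0% |
| 20% / 10% | 0.5 | 0.05 | 9% | 5.6% |
| 20% / 10% | 1.0 | 0.10 | 17% | 7.4% |
| 30% / 10% | 1.0 | 0.20 | 35% | 14% |

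For the third row: n₁ = 38.4, n₂ = 43.2, SE = 0.222 and 0.10/0.222 = 0.45. The error is P(Z > 1.96 − 0.45) + P(Z < −1.96 − 0.45) ≈ 0.066 + 0.008 = 0.074.

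**4. Power, if 96 counts families assigned rather than surveys returned.** With d = 0.572 and equal refusal in both arms:

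| Refusal (assumed) | Completers per arm | Power | Assigned total needed for 96 completers |
|---|---|---|---|
| 5% | 45.6 | 78% | 102 |
| 10% | 43.2 | 76% | 108 |
| 20% | 38.4 | 71% | 120 |
| 30% | 33.6 | 65% | 138 |

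The last column is 2 × 48/(1 − r), with each arm rounded up. If 96 already means completers, this loss does not arise. At 100 per arm power would be 98%. Enrolling more restores power but leaves the bias in step 3 unchanged.

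**The case against.** The strongest reply is that silence is not a rule. There is a face-to-face conversation before surgery, and nothing says that a family objecting there would still be assigned. Withdrawal Procedures covers families who decline after surgery; it does not say that this is the only time to decline. Consent pages were not in the copy reviewed, so an information sheet with an opt-out cannot be excluded. This stands. A reader might infer that no family can decline before assignment, or that every refusal falls after it; the text supports only that no earlier agreement step is described and that refusals can fall after allocation.

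Two other stronger readings are tempting.

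- **A contradiction with Subject Selection**, which excludes patients under 18 and "non-English speaking patients and/or families to ensure that consent is valid". That sentence is about who is able to consent, not when. Both statements can be true.
- **A failure to obtain the patient's consent**, since the patient's progress is paged out but the family member completes the form. The subjects are described as family members, and the protocol states that no PHI is included. Whether the patient must also agree, and whether implied consent is acceptable, is for the IRB.

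It is also fair to say that the bias figures rest on invented rates, and that asking first does not stop a family from skipping the survey later. Both stand. The first limits any claim about size; the second is why the fix needs reporting by arm as well.

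**Conclusion.** The point holds as a matter of sequence. Consent Procedures states a rule, not merely a gap: the defining act of consent is a form completed after assignment and after the intervention, and those who do not complete it are removed. Membership of the analysed set is thus settled after randomisation, by a choice that knowledge of the pathway could influence.

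The size is unknown. In the assumed cases above the bias runs from nothing (equal refusal, same refuser profile) to 0.20 SD, about a third of the effect that 48 per arm would detect with 80% power. The plan contains no evidence that refusal will be high or will differ by arm, so these figures show what could go undetected; they are not a forecast. The point rests on the protocol's own wording and on the inference that assignment precedes the first page. It deserves correction mainly because the remedy is nearly free.

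**What to change.** - **Procedures and Consent Procedures.** State that at the day-of-surgery conversation already planned, the research team member obtains verbal agreement and records it on a log before the assignment is made, and that families who decline are not assigned. Completing the survey then signifies agreement to the survey only.
- **Withdrawal Procedures.** Replace removal with a rule that every assigned family stays on the log under its assigned arm. Report survey non-completion by arm. The form already has a group field for the research team, so assigned minus returned gives the count without adding identifiers to the survey.
- **Statistical Considerations.** Add a simple sensitivity analysis for missing surveys, for example recomputing the arm difference with non-completers assumed to differ from completers by a stated range, allowed to vary by arm. State whether 96 means families assigned or surveys completed.

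The cost is a wording amendment, one log entry per family and a short extra analysis. The downside is that some families will decline up front and not be assigned. Asking first moves refusals that would have occurred in either arm to before allocation. Later non-completion is reduced but not eliminated, so the report by arm is still needed.
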